7.4. Analysis Populations

7.4.1. Intent-to-Treat Population

For the pilot study, the intent-to-treat (ITT) population will include all participants who received the study device and completed at least one post-baseline assessment of efficacy.

For the comparative study, the ITT population will include all participants who were randomized, received the study device or underwent neurectomy, and completed at least one post-baseline assessment of efficacy.

The ITT population will be the analysis population for the primary endpoint. Treatment assignment will be based on the treatment as randomized.

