5.5.1 Intent-To-Treat Population

The ITT population will include all subjects who were randomized, received the study device or underwent neurectomy, and completed at least one post-baseline assessment of efficacy. Subjects will be analyzed in the group to which they were randomized. The ITT population will be used for analyses of accountability, demographics, efficacy (superiority testing), and the calculation of the 95% confidence interval about the mean VAS change in the Axoguard® Nerve Cap group for the testing of the null hypothesis H_{0B}.

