7.3. Handling of Missing Data and Protocol Violations

Every effort will be made to obtain the VAS pain score data at each scheduled evaluation from all participants who have been randomized, especially at 12 months, since this is the primary efficacy endpoint (PEE). Missing data will be imputed for the primary endpoint only.

All other endpoints will be analyzed with the data available.

No accommodation will be made for a treatment protocol violation unless the proportion of major violations exceeds 5%. In this case, a sensitivity analysis will be done for the primary endpoint only comparing the results when all participants are included, and when those with major protocol violations are excluded. If the results differ, the analysis with the participants included will be the primary analysis.

Major protocol violations include:

- 1. Treating the participant with a non-study treatment or with a study treatment to which the participant was not randomized.
- 2. Assessing an endpoint by a method other than described in the clinical investigational plan (CIP).
- 3. Failing to report a primary endpoint for any reason other than the death of the participant or the participant leaves the study unrelated to the study treatment.

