7.4.2. Modified Intent-to-Treat Population

For the comparative study, the modified intent-to-treat (mITT) population will be the subset of the ITT population who completed at least one post-baseline assessment of efficacy. Treatment assignment will be based on the treatment as received.

The mITT population will be the primary analysis population for the secondary and tertiary endpoints. It will also be one of the analysis populations for the sensitivity analysis of the primary endpoint by running the analysis with the ITT population and then with the mITT population.

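### The comparative-phase ITT population leaves out some randomised subjects, and the mITT population has the same members, so comparing the two cannot test those exclusions

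*SAP*

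**What the plan says.** For the comparative study, SAP 7.4.1 defines the ITT population as "all participants who were randomized, received the study device or underwent neurectomy, and completed at least one post-baseline assessment of efficacy". It adds that "The ITT population will be the analysis population for the primary endpoint" and that "Treatment assignment will be based on the treatment as randomized". Protocol 5.5.1 has the same definition, "all subjects who were randomized, received the study device or underwent neurectomy, and completed at least one post-baseline assessment of efficacy", and uses the set for superiority testing, which is what Protocol 5.10 makes the criterion for study success.

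SAP 7.4.2 defines the mITT population as "the subset of the ITT population who completed at least one post-baseline assessment of efficacy", and there "Treatment assignment will be based on the treatment as received". The mITT is the primary set for secondary and tertiary endpoints. It also serves a sensitivity analysis of the primary endpoint, "by running the analysis with the ITT population and then with the mITT population". SAP 7.4.3 draws the per-protocol set from the mITT.

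On missing data, SAP 7.3 says: "Missing data will be imputed for the primary endpoint only".

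**The concern.** An intent-to-treat set keeps everyone who was randomised, because any condition met or failed after randomisation can differ between arms and break the comparability that randomisation created. This ITT has two such conditions: being treated, and having at least one post-baseline efficacy assessment. Protocol 3.4.4.4 rules out replacing randomised subjects, so anyone failing either condition is lost to the primary comparison.

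Normally a comparison between the full randomised set and a modified set shows whether such losses matter. Here the modified set repeats a condition of the full one, so the comparison has no excluded subjects to bring back. At stake is the primary VAS comparison at Month 12, with an exclusion effect that the ITT-versus-mITT run cannot reveal.

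**Working it through.** **Inputs.** ITT and mITT definitions: SAP 7.4.1 and 7.4.2, Protocol 5.5.1. Sample size: 86 randomised (SAP 7.1), allocated 1:1 (SAP 7.2), so 86 / 2 = 43 per arm. The derivation of 86 is not in the available text and is not needed here.

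**Step 1: membership.** Let R = randomised, T = treated (device or neurectomy), P = at least one post-baseline efficacy assessment.

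- SAP and protocol ITT = R and T and P
- SAP mITT = ITT and P = R and T and P
- Full intent-to-treat = R

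Among randomised subjects there are four cases:

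| Treated | Assessed | Full intent-to-treat | Plan's ITT | Plan's mITT |
|---|---|---|---|---|
| yes | yes | in | in | in |
| yes | no | in | out | out |
| no | yes | in | out | out |
| no | no | in | out | out |

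The four combinations with R = 0 are outside all three sets. ITT and mITT therefore differ in 0 of 8 combinations, and the ITT drops 3 of the 4 that belong in a full intent-to-treat set.

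**Step 2: what the sensitivity analysis can detect.** With the same members in both runs, the result can change only through subjects who received the other arm's treatment. The per-protocol set lies inside the mITT, so it does not restore anyone either.

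**Step 3: the other analysis that might help.** SAP 7.3 plans a primary-endpoint comparison with and without major violators, and failing to report a primary endpoint counts as a major violation, with exceptions. It runs only if major violations exceed 5%: 0.05 × 86 = 4.3, so at least 5 subjects. Its inclusive run could mean all randomised subjects or only the ITT set. Either way it does not redefine the ITT.

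**Step 4: size, by assumption.** No document gives a rate of untreated or never-assessed subjects. If the rate were 2%, 5%, 10% or 15%, the number analysed out of 86 would be about 84, 82, 77 or 73.

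If k of 43 in one arm are excluded and their mean change is d mm worse than that of those kept, the arm mean over all randomised differs from the analysed mean by k × d / 43:

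- k = 1, d = 20: 20 / 43 = 0.47 mm
- k = 2, d = 30: 60 / 43 = 1.40 mm
- k = 4, d = 40: 160 / 43 = 3.72 mm
- k = 6, d = 40: 240 / 43 = 5.58 mm

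The range is about 0.5 to 5.6 mm. Protocol 1.1 cites a minimum clinically significant reduction of 14 to 20 mm.

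**The case against.** The best reply is that almost nobody will be excluded. Randomisation is intra-operative, after eligibility is confirmed (Protocol 3.4.4.2 and 3.9), and acceptability for either treatment is decided beforehand (SAP 7.2). Both arms undergo neurectomy, so a cap-arm subject who never receives the cap still meets the treatment condition. VAS and PROMIS are collected at Week 2, and one score appears enough to stay in. Early-termination data are sought (Protocol 3.4.4.3), and assessments may be captured remotely (Protocol 3.10.2). All of this stands. It limits the size of the problem but does not change the definition.

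A second reply is that relabelling alone would recover little. That also stands. Most added subjects would have baseline VAS only, and an imputation assuming data missing at random would give them roughly their arm's expected change. The redefinition therefore needs a stated method and a sensitivity analysis.

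A reader might also infer several stronger things:

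- **That an unblinded surgeon chooses whom to exclude.** The surgeon does know the arm, and Protocol 3.4.4.3 lets the investigator, in consultation with the sponsor, discontinue a subject. But no section gives the surgeon a decision over population membership, and the VAS is marked by a blinded subject.
- **That no planned analysis could touch the excluded subjects.** SAP 7.3 offers possible cover, though it is conditional and its reach is unclear.
- **That the SAP intended the mITT to test exclusions.** It states no such purpose, and the contrast between as-randomised and as-received assignment is a real one.

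**Conclusion.** The point holds on the wording. The comparative-phase ITT is narrower than all randomised subjects in both documents, the mITT has exactly the same members, and the planned comparison between them does not test post-randomisation exclusions. This does not apply to the pilot, which is not randomised and has no mITT.

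The practical effect is probably small. The 0.5 to 5.6 mm range assumes 1 to 6 exclusions, all in one arm, with outcomes 20 to 40 mm worse; none of these figures comes from the documents. Even the upper end is below the 14 mm lower bound that the protocol cites, so it is unlikely to reverse a large effect but could matter for a borderline result. The documents do not support saying that the trial's result will be biased. They do support correcting the definitions, since a screening VAS is required for eligibility (Protocol 3.4.2) and primary-endpoint imputation is already promised.

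**What to change.** In Protocol 5.5.1 and SAP 7.4.1, define the comparative-phase ITT as all randomised subjects, analysed as randomised. State that missing Month 12 VAS, including for subjects with baseline only, is handled by the SAP's primary-endpoint imputation. Specify its method if the unredacted SAP does not, and reconcile it with the observed-data mixed model in Protocol 5.7.4. Add a sensitivity analysis that varies the assumed outcome of these subjects.

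In SAP 7.4.2, put both conditions in the mITT definition only: treated, and at least one post-baseline efficacy assessment. The treatment condition is needed because an untreated subject has no arm in an as-received analysis. The planned ITT-versus-mITT comparison would then test the exclusions. If any subject receives the other arm's treatment, an additional mITT run as randomised would separate the two effects.

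The cost is a few sentences in each document, a little more analysis work, and reliance on imputation for a few subjects. No new data are needed.

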7.4.2. Modified Intent-to-Treat Population

For the comparative study, the modified intent-to-treat (mITT) population will be the subset of the ITT population who completed at least one post-baseline assessment of efficacy. Treatment assignment will be based on the treatment as received.

The mITT population will be the primary analysis population for the secondary and tertiary endpoints. It will also be one of the analysis populations for the sensitivity analysis of the primary endpoint by running the analysis with the ITT population and then with the mITT population.

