7.4.3. Per-Protocol Population

For the comparative study, the per-protocol (PP) population will include all participants in the mITT population who have an endpoint for the analysis in question and have experienced no conditions that may confound study outcomes, such as sustaining a foot injury during study follow-up. Treatment assignment will be based on the treatment as received. If there are no participants with confounding events or conditions, this population will not be used.

The PP population will be the analysis population for sensitivity analyses of all endpoints by running the analyses with the primary (default) population (either the ITT or mITT) and then again with the PP.

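### The SAP's modified ITT population is the ITT population regrouped by treatment received, so the visible plan has no as-randomised analysis of the secondary efficacy endpoints

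*SAP*

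**What the plan says.** For the comparative phase, SAP 7.4.1 limits ITT to randomised participants who "received the study device or underwent neurectomy, and completed at least one post-baseline assessment of efficacy", grouped as randomised. Its use is stated: "The ITT population will be the analysis population for the primary endpoint".

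SAP 7.4.2 then says that "the modified intent-to-treat (mITT) population will be the subset of the ITT population who completed at least one post-baseline assessment of efficacy", and adds "Treatment assignment will be based on the treatment as received". On use: "The mITT population will be the primary analysis population for the secondary and tertiary endpoints". A comparison of ITT with mITT is planned for the primary endpoint.

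SAP 7.4.3 takes the per-protocol (PP) population from mITT, restricted to those who "have an endpoint for the analysis in question" and who have no confounding condition. It is again grouped as received. "The PP population will be the analysis population for sensitivity analyses of all endpoints", but "If there are no participants with confounding events or conditions, this population will not be used".

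SAP 7.3 plans a comparison with and without major violators, for the primary endpoint only and only if major violations exceed 5%. SAP 8.1 defines treatment group by the procedure carried out. SAP 9.2.1 compares the secondary endpoints between treatment groups by t-tests and Fisher's exact test, and names no population.

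Protocol 5.5 lists ITT, safety and PP populations and has no mITT. Protocol 5.5.1 groups ITT as randomised.

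**The concern.** A modified ITT population normally drops some subjects and keeps the randomised grouping. This one drops nobody and changes the grouping, so the label describes an as-treated analysis.

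The secondary endpoints are between-arm tests, so the grouping rule determines the result whenever a participant receives the other procedure. If such switches are related to prognosis, for example because a difficult nerve stump leads the surgeon away from the device, the groups being compared are no longer those that randomisation made comparable. The visible plan would then offer no as-randomised result to set beside the secondary findings, and adding one after unblinding would be open to criticism.

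**Working it through.** **Membership.** Let R = randomised, T = treated with either procedure, and P = at least one post-baseline efficacy assessment. Under SAP 7.4.1, ITT = R and T and P. Under SAP 7.4.2, mITT = ITT and P = R and T and P. The two sets differ in 0 of the 8 combinations of R, T and P.

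**Possible routes to an as-randomised secondary analysis in the visible SAP.**
- 7.4.1: ITT is assigned to the primary endpoint.
- 7.4.2: the ITT-versus-mITT comparison is for the primary endpoint.
- 7.4.3: PP reaches all endpoints but is grouped as received. The default it is set against is mITT for the secondary endpoints.
- 7.3: the major-violation comparison is for the primary endpoint only. Its trigger is 0.05 × 86 = 4.3 subjects, so four crossovers (4/86 = 4.65%) with no other violation would not start it, while five (5/86 = 5.81%) would.
- 9.2.1: no population is named, and treatment group carries the 8.1 meaning.

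None provides one.

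**Size, on assumed values.** From the documents: 86 randomised 1:1, so 43 per arm, and the first secondary endpoint (PROMIS Pain Behavior, t-test). Assumed: no device effect; SD 10 T-score points within prognosis subgroup; k device-arm subjects receive neurectomy; these subjects, and k counterparts in the control arm, do d points worse than the rest.

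As received, the device group is 43 − k subjects, none with poor prognosis. The neurectomy group is 43 + k, of whom 2k have poor prognosis. Bias = 2kd/(43 + k), in favour of the device. As randomised, each arm has k of 43 with poor prognosis, so bias = kd/43 − kd/43 = 0.

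Rejection rates are for a two-sided 5% pooled t-test, 400,000 simulated trials per cell:

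| d | k | Bias as received | Rejection as received | Rejection as randomised |
|---|---|---|---|---|
| 5 | 1 | 10/44 = 0.23 | 5.0% | 4.9% |
| 5 | 2 | 20/45 = 0.44 | 5.4% | 4.9% |
| 5 | 4 | 40/47 = 0.85 | 6.4% | 4.7% |
| 10 | 1 | 20/44 = 0.45 | 5.2% | 4.8% |
| 10 | 2 | 40/45 = 0.89 | 6.4% | 4.5% |
| 10 | 4 | 80/47 = 1.70 | 10.7% | 4.2% |

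With d = 0, bias is 0 and rejection about 5.0% under either grouping. With d = 10 and SD 8 to 12, as-received rejection runs from 7.0% to 5.9% for k = 2 and from 13.5% to 9.0% for k = 4. The as-randomised rates just below 5% arise because exactly k poor-prognosis subjects were fixed in each arm; they are not a gain from that analysis.

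**The case against.** The best defence is that the practical weight is small, and most of it stands. Protocol 3.9 confirms eligibility during surgery before randomisation, and SAP 7.2 requires that suitability for either treatment be settled beforehand, so crossovers should be few. Without any, ITT and mITT give the same answer. The 10.7% figure needs 4 of 43 device subjects (9.3%) to switch in one direction, all a full SD worse. SD 10 is the T-score scaling in SAP section 6, not a documented SD of change. SAP 8.2 disclaims control of Type I error, so these rates describe bias in a single test, not a failed studywise guarantee. None of this supplies a reason to group secondary endpoints differently from the primary one.

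Some stronger readings are tempting.

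- A reader might infer that the SAP contradicts the protocol on the secondary endpoints. Protocol 5.5.1 assigns ITT to efficacy, with superiority testing in parentheses. The visible text under protocol 5.2 ties superiority to VAS. Protocol 5.7.1 tests secondary endpoints in sequence, which makes a broader reading possible, but it names no population. A direct conflict is not established, and protocol 5.2 leaves detailed methods to the SAP.
- A reader might infer that the primary result is compromised, given the SAP 8.1 definition. SAP 7.4.1 specifically says as randomised for the ITT population used there.
- A reader might extend the finding to the tertiary endpoints. The population rule covers them, but the body of SAP 9.4 is not visible.
- A reader might take the bias as always favouring the device. It reverses if the better-prognosis subjects switch.

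**Conclusion.** The point holds for the comparative-phase secondary efficacy endpoints in the visible SAP: mITT is an as-received regrouping of ITT, it is their primary population, and no as-randomised analysis of them is planned. SAP 8.1 reinforces this.

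The consequence depends on crossovers that relate to prognosis, and the documents give no rate for these. On the assumed values, one or two crossovers move the single-test rejection rate to between 5.0% and 6.4%; four move it to between 6.4% and 10.7%. Study success under protocol 5.10 rests on VAS and adverse events, so the secondary endpoints do not decide it. The change is worth making because it is nearly free, not because large bias is expected.

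There is a separate, minor point, on the visible text only. Protocol 5.5.3 makes PP, meaning no major violations, primary for the non-inferiority test of VAS, whereas SAP 7.4.1 assigns the primary endpoint to ITT. The PP definition in SAP 7.4.3 also differs, as it turns on confounding conditions and not on major violations. This does not depend on mITT and does not carry the main finding.

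**What to change.** - **SAP 7.4.2:** make ITT, grouped as randomised, the primary population for the secondary and tertiary efficacy endpoints, using available data as in 7.3. Delete mITT as a separate population. Keep as-received grouping as one labelled supportive efficacy analysis and for the Safety population.
- **SAP 7.4.3:** define PP from ITT instead of mITT, and state its grouping so that it agrees with 8.1 or is a labelled exception.
- **SAP 8.1:** define treatment group as randomised for efficacy and as received for safety. Otherwise 9.2.1 would still be read as received.

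The ITT definition itself stays as it is.

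The cost is SAP wording and table shells, with no new data. The downside is slight dilution if device-arm subjects cross over: the as-randomised estimate keeps (43 − k)/43 of the effect, that is 42/43 = 98%, 41/43 = 95% and 39/43 = 91% for k = 1, 2 and 4.

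For the separate point, reconcile protocol 5.5.3 with SAP 7.4.1 and 7.4.3, and report both ITT and PP for non-inferiority. Copying 5.5.3 into the SAP is not enough. SAP 7.3 says the analysis that includes violators is primary if the results differ. It also counts most failures to report the primary endpoint as major violations, while planning to impute missing primary-endpoint data. Those sentences must be settled at the same time.

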7.4.3. Per-Protocol Population

For the comparative study, the per-protocol (PP) population will include all participants in the mITT population who have an endpoint for the analysis in question and have experienced no conditions that may confound study outcomes, such as sustaining a foot injury during study follow-up. Treatment assignment will be based on the treatment as received. If there are no participants with confounding events or conditions, this population will not be used.

The PP population will be the analysis population for sensitivity analyses of all endpoints by running the analyses with the primary (default) population (either the ITT or mITT) and then again with the PP.

7.4.4. Safety Population

For the pilot study and comparative study, the safety population (SP) will include all participants who had the study device inserted or underwent neurectomy. This population will be used for all safety analyses. Treatment assignment will be based on the treatment received.

8. Analysis Methods

8.1. General

Data collected from each study part will be analyzed separately. Descriptive statistical methods will be used to summarize the data from this study. Unless stated otherwise, the term "descriptive statistics" refers to number of events (n), mean, median, standard deviation (SD), interquartile range (IQR), minimum, and maximum for continuous data and frequencies and percentages for categorical data.

The term 'treatment group' refers to the type of procedure conducted, either Axoguard Nerve Cap (AXOG) or Neurectomy (NEUR). All statistical analyses will be conducted with validated statistical software package like SAS or Stata.

8.2. Control of Type 1 Error

Type I error will not be controlled in this study in order to understand the potential benefits of Axoguard Nerve Cap regardless of the studywise error rate.

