5. STATISTICAL CONSIDERATIONS

Descriptive statistical methods will be used to summarize the data from this study. Unless stated otherwise, the term "descriptive statistics" refers to number of events (n), mean, median, standard deviation (SD), standard error, minimum, maximum, and coefficient of variation (CV) for continuous data and frequencies and percentages for categorical data. All data collected during the study will be included in data listings. Unless otherwise noted, the data will be sorted by subject number, and then by date within each subject number.

Unless specified otherwise, all statistical testing will be two-sided and will be performed using an overall significance (alpha) level of 0.05.

All statistical analyses will be conducted with the SAS® System, version 9.1.3 or higher.

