5.7 General Issues for Statistical Analysis

5.7.1 Multiple Comparisons and Multiplicity

All summaries of categorical data will be presented in frequencies and percentages. All summaries of continuous data will be presented by the number of non-missing values, mean, standard deviation, standard error, median, minimum, maximum, and coefficient of variation. Mann-Whitney U tests will be used to compare baseline data to ensure poolability across centers.

As the final data analysis is to be conducted using blinded group data, no adjustment for type I error is necessary for analysis. As the tests of non-inferiority and superiority are being performed in a closed testing procedure, there will be no adjustment for multiple secondary endpoints; a step-down procedure will be utilized in the assessment of the secondary efficacy endpoints:

- 1. VAS score at 1, 3, 6, 9 and 12 months compared to baseline
- 2. PROMIS® score at 1, 3, 6, 9 and 12 months compared to baseline
- 3. FHSQ score at 1, 3, 6, 9 and 12 months compared to baseline
- 4. Quantity, quality and class of pain medication use at 1, 3, 6, 9 and 12 months compared to baseline

Quantity class of pain medication used for end-neuroma pain

Rate of recurrence of symptomatic neuroma

For this procedure, the hypotheses will be tested sequentially based on the specified ordering. Statistical testing will continue at the =0.05 level until a p-value greater than 0.05 is observed.

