5.8.2 Secondary Efficacy Endpoints

The secondary efficacy endpoints for the comparative study are VAS, PROMIS® and FHSQ scores at months 1, 3, 6, 9 and 12 compared to baseline; and quantity and class of pain medication use at months 1, 3, 6, 9, and 12 months compared to baseline for subjects assigned to the Axoguard® Nerve Cap. The secondary efficacy endpoints for the comparative study are VAS, PROMIS® and FHSQ scores at months 1, 3, 6, 9 and 12 compared to baseline; and quantity, quality and class of pain medication use at months 1, 3, 6, 9, and 12 months compared to baseline for subjects in both the Axoguard® Nerve Cap study arm and the historical control neurectomy study arm.

All secondary endpoints will be summarized using descriptive statistics by repair type and by study day/time, if appropriate.

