5.10 Study Success

Study success is defined as demonstrating the reduction in pain by VAS score with the treatment of Axoguard® Nerve Cap is superior to the reduction in VAS score for neurectomy group

In addition, there should be no clinically significant difference of product related adverse events rates following implantation of Axoguard® Nerve Cap compared to neurectomy.

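### The protocol prescribes a step-down at 0.05 for the secondary endpoints, the SAP disclaims type I error control, and neither says which rule governs a claim of significance

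*SAP*

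**What the plan says.** **Protocol.** Section 5: "Unless specified otherwise, all statistical testing will be two-sided and will be performed using an overall significance (alpha) level of 0.05". Section 5.7.1 first says that "no adjustment for type I error is necessary for analysis", on the ground that the final analysis uses blinded group data. It then says "there will be no adjustment for multiple secondary endpoints; a step-down procedure will be utilized in the assessment of the secondary efficacy endpoints", and adds "For this procedure, the hypotheses will be tested sequentially based on the specified ordering", at the 0.05 level, "until a p-value greater than 0.05 is observed". The list has four numbered items (VAS, PROMIS, FHSQ, pain medication), each at Months 1, 3, 6, 9 and 12, and ends with recurrence. Section 5.8.2 mentions only summaries: "All secondary endpoints will be summarized using descriptive statistics by repair type". Section 5.10: "Study success is defined as demonstrating the reduction in pain by VAS score" is superior to that with neurectomy, together with a condition on adverse events.

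**SAP.** Section 8.2: "Type I error will not be controlled in this study in order to understand the potential benefits of Axoguard Nerve Cap", whatever the resulting error rate across the study. Section 9.1.2 keeps closed testing of non-inferiority and superiority for the primary endpoint. Section 9.2.1 lists six numbered rows:
- rows 1 to 4: change from baseline to Month 12 in PROMIS Pain Behavior, FHSQ General Foot Health, morphine equivalents (MME) and Medication Quantification Scale (MQS) score, each by t-test;
- row 5: recurrence at Month 12, by Fisher's exact test;
- row 6: AUC of diary and VAS scores, by t-test or another test to be chosen.

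**The concern.** A secondary p-value below 0.05 means different things under the two documents. Under Protocol 5.7.1 it is a confirmed finding if every earlier step succeeded. Under SAP 8.2 it is one of several uncontrolled tests. As neither rule has stated precedence, the choice could be made after the results are known, and the label on the secondary results would then depend on how they turned out.

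Two smaller matters sit in the same table. Rows 1 to 4 compare changes from baseline without adjusting for the baseline value, which can waste precision in a trial of 86. Row 6 does not say how an AUC is computed, whether diary and VAS give one test or two, or how a subject who leaves early counts; SAP 7.3 says only that available data are used.

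**Working it through.** **1. Does either document settle the matter alone?**

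| | Protocol 5.7.1 | SAP 8.2 and 9.2.1 |
|---|---|---|
| Error policy | Step-down at 0.05 | No control |
| Order | Specified list | Rows numbered 1 to 6, never called a sequence |
| Stopping rule | First p above 0.05 | None |
| First entry | VAS at five visits | PROMIS Pain Behavior, Month 12 |
| AUC | Absent | Row 6 |
| Medication | One item | MME and MQS separately |

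The protocol's items 1 to 4 hold 4 × 5 = 20 visit-level hypotheses with no order within an item, so its step-down is incomplete as written. Rows 1 to 5 of the SAP do follow the protocol's family order (PROMIS, FHSQ, medication, recurrence), narrowed to Month 12. No sentence makes that a testing order.

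**2. Error rates.** Inputs: 0.05 two-sided (Protocol 5) and six rows (SAP 9.2.1).
- Protocol rule, with a complete fixed order: with no true effect, a false claim requires the first step to reject, so the rate is 0.05. The protocol's figure is reproduced.
- Six independent tests: 1 − 0.95^6 = 0.265. If row 6 is two tests: 1 − 0.95^7 = 0.302.
- Equicorrelated normal statistics (the correlations are assumptions; the documents give none):

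| Correlation | Six tests | Seven tests |
|---|---|---|
| 0.3 | 24.1% | 27.1% |
| 0.5 | 20.7% | 23.0% |
| 0.7 | 16.4% | 17.8% |

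- Fisher's test is conservative. With 43 per arm (86 ÷ 2) its true size is 0.02% to 3.03% at assumed recurrence of 2% to 30%. The six-test independent figure is then 1 − 0.95^5 × (1 − size) = 22.6% to 25.0%.

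**3. Where recurrence would stand in a sequence.** SAP 6 requires three conditions together, including a VAS above baseline, so recurrence may be uncommon. With 43 per arm, 0 v 5 events gives p = 0.055 and 0 v 6 gives p = 0.026. Exact power, assuming the device halves the control rate:

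| Control rate | Power |
|---|---|
| 5% | 0.7% |
| 10% | 5.1% |
| 20% | 16.9% |
| 30% | 29.6% |

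Take a sequence gated on the primary, with recurrence before two AUCs, and assume independence and 80% power at each of the seven other steps. The last AUC is claimable with probability 0.8^7 × power = 0.210 × power, which is 0.1% to 6.2%. With recurrence last, the same AUC is claimable in 0.8^7 = 21% of trials.

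**4. Baseline adjustment.** Let r be the correlation of baseline with follow-up and s the ratio of baseline SD to follow-up SD. Adjusted variance over change-score variance is (1 − r²)/(1 + s² − 2rs).

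| s | r = 0.3 | r = 0.6 |
|---|---|---|
| 1.0 | 0.65 | 0.80 |
| 0.8 | 0.78 | 0.94 |
| 0.6 | 0.91 | 1.00 |

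Estimating the covariate costs a factor of about 1 + 1/82 = 1.012.

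**5. AUC, illustration only.** Assume that pain falls linearly from 80 to 20 mm by Day 180 and is then flat. Assume no true effect, and dropout of 20% with the device and 5% without, unrelated to pain. Leavers' last visit is Day 30, 90, 180 or 270 with probability 0.2, 0.3, 0.3, 0.2.
- Complete AUC: (9000 + 3600)/360 = 35.0 mm.
- Sum to last visit, over 360 days: areas 2250, 5850, 9000, 10800, mean 7065, or 19.6 mm. The shortfall of 15.4 mm × 0.15 gives a bias of −2.3 mm.
- Sum over observed time: averages 75, 65, 50, 40, mean 57.5. The excess of 22.5 mm × 0.15 gives +3.4 mm.
- Only subjects with a complete AUC: no bias under these assumptions.

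**The case against.** The strongest defence is that SAP 8.2 states a deliberate choice openly, in a study that the SAP calls post-market, and that success under Protocol 5.10 uses no secondary endpoint. The SAP is also the more detailed document and names protocol version 3.0, so it might be taken to supersede 5.7.1. The first part stands and limits the harm to secondary claims. The second does not: no text gives the SAP precedence or declares a departure from 5.7.1. Even on that reading the step-down would have to be deleted and the p-values labelled nominal.

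It is also fair to say that the rows are numbered, that rows 1 to 5 keep the protocol's family order, and that four endpoint families are shared. A reader might infer that the SAP has no order at all and tests different endpoints. That goes too far; what is missing is a statement that the numbering is a sequence.

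A reader might also infer that the trial's main conclusion carries a 26.5% false-positive risk. It does not. That figure concerns the six secondary rows only, although the study-wide wording of 8.2 sits awkwardly beside the closed testing in SAP 9.1.2.

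On the smaller points, the unadjusted t-test is valid under randomization, and adjustment gains nothing at one end of the assumed range. Protocol 5.7.2 on covariates is incomplete in the text available, so the point rests on the SAP table alone. The AUC figures depend on assumed dropout and decline, are small beside the 14 to 20 mm clinically significant difference in Protocol 1.1, and do not arise if only complete AUCs are used and dropout is unrelated to pain. They are no forecast of bias in this trial.

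**Conclusion.** The conflict is real and should be resolved, but it is confined to the secondary results. With six rows each tested at 0.05 and no true effect, the chance of at least one false positive is 26.5% if independent and 16.4% to 24.1% at assumed correlations of 0.7 to 0.3. A complete fixed sequence gives 5%. Neither document alone yields a usable rule: the SAP states none, and the protocol's list is incomplete and does not match the SAP rows. The primary conclusion and study success stand apart from this.

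Baseline adjustment is a question of precision, not of error rate: 0% to 35% less variance over the assumed range, less about 1% for the extra covariate. The undefined AUC is a minor gap.

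**What to change.** **1. State one policy in both documents before unblinding.** Either:
- (a) keep SAP 8.2, delete the step-down from Protocol 5.7.1, label every secondary p-value nominal and call no secondary result significant; or
- (b) replace SAP 8.2 with one complete fixed sequence over the SAP rows, one hypothesis per step at two-sided 0.05, with results after the first failure descriptive. Report all estimates and 95% confidence intervals, which preserves the stated aim of 8.2. Align Protocol 5.7.1 and 5.8.2.

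Under (b) the sponsor chooses the order and decides whether to require primary superiority first; neither document contains such a gate. Recurrence should come last, because its low power would block whatever follows.

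Option (a) costs only wording, but gives up secondary claims. Option (b) allows fewer claims than testing every row freely, and none if a gate is used and the primary fails. VAS at Months 1, 3, 6 and 9, which heads the protocol's list, becomes descriptive unless it is added to the sequence.

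**2. Rows 1 to 4.** Use ANCOVA with the baseline value as covariate. First fix one baseline assessment per endpoint, since SAP 6 allows either Day 0 or the screening period. The data are already collected, so the cost is minor programming.

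**3. Row 6.** Say whether diary and VAS are separate hypotheses, how each AUC is computed, which test is used, and how early leavers are handled. Do not use a raw sum to the last visit or a sum divided by observed time.
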